### **9.3.4 Efficacy Analyses**

Preliminary efficacy will be evaluated as a secondary objective of the study by comparing between dose groups the following endoscopic and histologic measures of disease activity. Change from baseline to Day 57 will be analyzed and reported descriptively.

- Change from baseline to Day 57 (and descriptively at Day 29) in endoscopic indices of disease activity (Ulcerative Colitis Endoscopic Index of Severity [UCEIS] and MCS-ES)
- Change from baseline to Day 57 (and descriptively at Day 29) in histology score of sigmoid colon biopsies (GS, RHI, and Nancy Histology Index [NHI])

In addition, preliminary efficacy will also be evaluated by comparing overall disease activity between dose groups using:

- Change from baseline to Day 57 (and descriptively at Day 29) in MCS

The main foreseen intercurrent event for this study is early treatment discontinuation. In the scenario that no intercurrent events occur (i.e., all participants complete the expected number of doses), the estimand is uncontroversial as simply the mean difference between treatment groups in change from baseline to Day 57 in efficacy scores. If however, intercurrent events are observed, three different strategies will be employed to handle early treatment discontinuation, each leading to their own respective estimands.

A treatment policy strategy (ITT population) will be used to estimate the difference between dose groups in the change from baseline in endoscopy, histology and overall disease activity scores, regardless of whether early treatment discontinuation occurred. In the absence of missing data, this can be achieved using Analysis of Covariance (ANCOVA) with dose group as a factor, otherwise an imputation method will be applied as appropriate.

A composite strategy (ITT population) will be used for endoscopy and overall disease activity scores to estimate the difference in the proportion of responders between dose groups, where responders are defined as those participants who reach a threshold of change from baseline in efficacy scores, in the absence of early treatment discontinuation. Endoscopic response is defined as at least a 1 point decrease in the MCS-ES and at least a 3 point decrease in the UCEIS. Clinical response (overall disease activity) is defined as at least a 3 point and 30% decrease from baseline in the MCS. MCS remission is a stool frequency score of 1 or 0 (with at least a 1 point decrease), a rectal bleeding score of 0, and an endoscopy score of 1 or 0 but with no friability. Endoscopic remission will be defined as a UCEIS score of 1 or 0. Treatment failure is defined as non-response or early treatment discontinuation. In the absence of missing data this can be analyzed using logistic regression with dose group as a factor, otherwise an imputation method will be applied as appropriate.

An on-treatment strategy (PP population) will be used to estimate the difference between dose groups in the change from baseline in endoscopy, histological and overall disease activity scores, restricted to those participants who completed the expected number of doses of their randomly assigned treatment. In the absence of missing data this can be achieved using ANCOVA with dose group as a factor, otherwise an imputation method will be applied as appropriate.

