#### **4.1.1 Length of the Study**

The total duration of the study for each participant will be approximately 19 weeks divided as follows:

- Screening: Up to 5 weeks (35 days).
- Dosing Period: Day 1 to Day 43.
- In-clinic period: From Day –1 to Day 2 for first dose, from Day 15 to Day 16 for the second dose, from Day 29 to Day 30 for the third dose, and from Day 43 to Day 44 for the last dose.
- Final follow-up: Day  $99 \pm 3$  days (8 weeks post last dose).

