#### **4.1.4 Individual Participant Stopping Criteria**

Dosing will be stopped in a given individual participant if, compared with baseline, one of the following circumstances occurs:

- *A second systemic IRR or hypersensitivity AE of any grade occurs (see Sections 4.1.5 and 8.3.8).*
- Grade 3 or greater severe AE or SAE considered related to study drug, including but not limited to:
  - *IRR/ hypersensitivity reaction which is considered related to study drug and believed to pose an unacceptable risk if the dose is repeated.*
  - *CLS including severe, clinically significant respiratory distress syndrome, edema, effusions, or decrease in blood pressure*
- Disease exacerbation requiring escalation of baseline treatment or other treatment strategies (pharmacological or surgical) signifying study treatment failure (See Section 7).
- Development of neutralizing antibodies to recombinant human IL-2 (also see study stopping criteria Section 4.1.3).
- Other findings that, at the discretion of the Investigator, indicate that dosing should be stopped.

Study closure information is provided in [Appendix 1](#).

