### **6.5.2 Prohibited Therapy**

All medications (prescription and OTC) taken within 30 days of study screening will be recorded on the appropriate eCRF.

As a general rule, no concomitant medication will be permitted, with the exception of medications to treat AEs and those specified (Section 6.5.1), unless the rationale for exception is discussed and clearly documented between the Investigator and the Sponsor.

Use of the following therapies will be prohibited during the study and for at least 14 days or at least 5 half-lives prior to initiation of study treatment, whichever is longer unless otherwise specified below:

- Unless covered by the exceptions described in Section 6.5.1:
  - Any rectal therapy.
  - Doses of glucocorticoids exceeding 20 mg/day of prednisone or equivalent
  - Non-steroidal anti-inflammatory medications (e.g., ibuprofen, naproxen) due to a propensity for these treatments to worsen inflammation in ulcerative colitis.
- Calcineurin inhibitors (e.g., tacrolimus, cyclosporine) and any other immune system targeted biological therapy 12 weeks or 5 half-lives, whichever is longer, before the start of screening.

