**Table 6 Analysis Populations**

Population	Description
Intent-to-treat (ITT)	All randomized participants will be included in the intent-to-treat population.
Per-protocol (PP)	All randomized participants that received the expected number of doses will be included in the per-protocol population.
Safety	All participants randomized to study treatment and who received at least one dose of the study treatment, whether prematurely withdrawn from the study or not, will be included in the safety analysis.
Pharmacokinetic	Participants who have received active treatment will be included in the PK analysis population. Participants will be excluded from the PK analysis population if they significantly violate the inclusion or exclusion criteria, deviate significantly from the protocol, or if data are unavailable or incomplete which may influence the PK analysis. Excluded cases will be documented together with the reason for exclusion. All decisions on exclusions from the analysis will be made prior to database closure.
Efficacy	Participants who were included in the ITT population.
Pharmacodynamic	Participants who were included in the Safety analysis population.
Biomarker	Participants who were included in the Safety analysis population.
Immunogenicity	Participants who had at least one pre-dose and one post-dose ADA assessment will be included and analyzed according to the treatment they actually received. In first instance, only samples from RO7049665-treated participants will be analyzed. The relationship between ADA status and safety, efficacy, PK, and biomarker endpoints will be analyzed and reported descriptively.

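### A participant whose colitis therapy is escalated after the fourth dose but before Day 57 stays in the per-protocol set and can count as a responder

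*Combined protocol and SAP*

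**What the plan says.** Section 9.3.4 names one intercurrent event: "The main foreseen intercurrent event for this study is early treatment discontinuation". It treats a trial in which everyone receives all planned doses as one without intercurrent events. For other cases it states that "three different strategies will be employed to handle early treatment discontinuation, each leading to their own respective estimands".

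- **Composite strategy.** A responder must "reach a threshold of change from baseline in efficacy scores, in the absence of early treatment discontinuation". The matching failure rule is "Treatment failure is defined as non-response or early treatment discontinuation".
- **On-treatment strategy.** It uses the PP set, which Table 6 defines by dose count: "All randomized participants that received the expected number of doses will be included in the per-protocol population".
- **Treatment policy strategy.** It uses all randomised participants whether or not they discontinued.

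The timetable in Section 4.1.1 reads "Dosing Period: Day 1 to Day 43". The efficacy endpoint is Day 57.

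Section 4.1.4 lists, among the reasons to stop dosing in an individual, "Disease exacerbation requiring escalation of baseline treatment or other treatment strategies (pharmacological or surgical) signifying study treatment failure". Section 8.2.8 gives the exacerbation criterion (partial Mayo score more than 2 points above baseline at two visits in a row) and leaves treatment to the treating physician's judgement. Section 6.5.2 prohibits certain therapies during the study, but does not say how their use affects response status or PP membership. Section 9.5 provides for a listing of protocol deviations.

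**The concern.** Up to the fourth dose, Sections 4.1.4 and 9.3.4 work together. A flare that needs escalation stops dosing, and stopped dosing is early discontinuation, so the participant is a composite failure and leaves the PP set. After the fourth dose there is no dosing left to stop. The same flare, treated in the same way, is then not an intercurrent event at all.

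The effect of the rescue is credited to the randomised arm. If rescue for flares is commoner on placebo, it hides a drug effect; if it falls on active participants, it inflates one. The composite and on-treatment analyses are the two that are meant to separate the drug's effect from what happens when treatment fails, so the gap matters most there. Section 2.1 says that the results will support further development.

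**Working it through.** The plan gives no figure for rescue. Its only sample-size figures are the adverse event (AE) detection probabilities in Section 9.2. They reproduce (1 − 0.8^8 = 83.2%, stated 83%; 1 − 0.8^4 = 59.0%, stated 59%) but do not bear on this point. The check is therefore a trace through the rules, followed by arithmetic on the planned group sizes.

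**1. Trace through Sections 4.1.4 and 9.3.4 and Table 6**

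| Participant | Composite status | PP set |
|---|---|---|
| Flare with escalation, dosing stopped before dose 4 | Failure | Out |
| All 4 doses, escalated after Day 43, Day 57 scores below threshold | Failure (non-response) | In |
| All 4 doses, escalated after Day 43, Day 57 scores reach threshold | Responder | In |
| UC therapy added or prohibited therapy used, no dose missed, threshold reached | Responder | In |

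The last three rows show the gap. PP retention occurs whatever the scores; misclassification as a responder occurs only if the threshold is reached.

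**2. Time available**

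- Last dose to endpoint: 57 − 43 = 14 days.
- Table 1 schedules the partial Mayo score on Days 43, 50 and 57. Section 8.10.2 puts dosing-day assessments before the dose, so a flare confirmed by Day 43 can still stop dose 4.
- A flare shown at Days 43 and 50 is confirmed on Day 50, which leaves 57 − 50 = 7 days. Only unscheduled visits, or escalation outside the Section 8.2.8 criterion, use more of the 14 days.

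**3. How far scores must move**

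- A rise of more than 2 on a whole-number score is at least 3 points above baseline.
- Clinical response needs the full Mayo score at least 3 points and 30% below baseline. The partial score has a maximum of 9, so one that rises by 3 starts at 6 or less. Baseline Mayo is then at most 6 + 3 = 9; 30% of 9 is 2.7, so the 3-point rule binds.
- If the endoscopy subscore falls by 1, the partial score must end 2 below baseline, a swing of 3 + 2 = 5 points. If it falls by 2 the swing is 4, and if it falls by 3 the swing is 3.
- Endoscopic response and endoscopic remission have no symptom component, so they do not require this reversal.

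**4. Effect of one case**

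- At 4:1, 65 participants give 65/5 = 13 placebo and 52 active. Pooling placebo across dose levels is my assumption.
- One reclassified placebo participant: 1/13 = 7.7 points. One in a dose level of two full cohorts (16 active): 1/16 = 6.3 points.
- Illustration with assumed counts, 8/16 active and 4/13 pooled placebo responders. As written, the difference is 50.0 − 30.8 = 19.2 points. If one active responder had been rescued and is counted as a failure, it is 7/16 − 4/13 = 13.0. If one placebo responder had been rescued, it is 8/16 − 3/13 = 26.9. If two had, it is 8/16 − 2/13 = 34.6.

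**5. How many might be rescued late**

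No rate is given. For assumed rates of 2%, 5%, 10% and 15% per participant, the expected number among 65 is 1.3, 3.3, 6.5 and 9.8. The chance of at least one among 13 placebo participants, 1 − (1 − r)^13, is 23%, 49%, 75% and 88%. These count rescues. Misclassified responders are a subset, and step 3 suggests a small one for clinical response.

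**The case against.** Several stronger readings are tempting, and the documents do not support them.

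- **That early discontinuation is the only route to failure.** Non-response is also failure, so a participant still flaring at Day 57 is classified correctly. Only the composite strategy defines failure.
- **That all three estimands are at fault.** Treatment policy uses data after rescue by design.
- **That Sections 4.1.4 and 9.3.4 contradict each other.** One is a dose-stopping rule and the other an analysis definition. They agree while doses remain; afterwards there is a gap.
- **That steroid given for drug-caused AEs creates an apparent effect.** Section 6.5.2 does say "no concomitant medication will be permitted, with the exception of medications to treat AEs", but it also prohibits rectal therapy and glucocorticoid above 20 mg/day prednisone equivalent unless excepted in Section 6.5.1. That section names paracetamol and antihistamines for systemic reactions, not steroid. How the AE exception and the steroid limit fit together is unclear. A related Grade 3 or higher AE, or a second systemic reaction, stops dosing under Section 4.1.4. No frequency of such steroid use is given, so this route is speculative.
- **That one case moves a rate by 12.5 or 50 points.** Those are per-cohort figures (1/8 and 1/2). Section 9.3.4 compares dose groups, and a dose level may hold several cohorts.

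It can also be said that rescue will be visible in the concomitant-medication listings, that few late-rescued participants will reach a response threshold in about 7 days, and that efficacy is preliminary with no hypothesis or power. All of that stands and limits the size of the problem. It does not close the gap: a listing does not change a participant's classification, and PP retention does not depend on improvement.

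**Conclusion.** The point holds. Under Section 9.3.4 and Table 6, a participant with all four doses whose UC therapy is escalated before the Day 57 assessment remains in the PP set and, with qualifying scores, is a responder or remitter. The same applies to UC therapy started or increased, or prohibited therapy used, without a missed dose. I found nothing elsewhere in the documents that prevents it.

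The number affected is unknown and probably small. The size per case is about 7.7 points in a pooled placebo group of 13, assuming full enrolment, exact 4:1 allocation and pooling. The conclusion also assumes that the participant attends Day 57; one who leaves earlier has a missing endpoint, for which the imputation method is not specified. Because efficacy is secondary and descriptive, this is a change that should be made before unblinded efficacy analysis, not a threat to the trial's primary safety purpose.

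**What to change.** In Section 9.3.4, add a second intercurrent event: start of therapy for UC, or its increase above the baseline dose, after the first dose and before the Day 57 assessment, whether or not all doses were given. Include rectal therapy, glucocorticoid above the Section 6.5.2 limit, and surgery. Then state:

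- **Composite:** these participants are non-responders and non-remitters.
- **On-treatment:** they, or their data after rescue, are excluded.
- **Treatment policy:** unchanged.
- **Corticosteroid given only for a non-UC AE:** flag it and examine it in a sensitivity analysis. Counting it automatically as failure could bias against the drug if such AEs are commoner on active treatment.
- **Data source:** use both the Concomitant Medications and the Adverse Event eCRFs, since Section 6.5.1 directs AE treatments to the latter.

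Reconcile the failure definition in Section 9.3.4 with the wording in Section 4.1.4. None of this changes who may receive rescue.

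The cost is a paragraph of analysis text and a medication flag built from data already collected. Response rates may be slightly lower and the PP set slightly smaller.

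### If early discontinuation occurs, the responder analysis targets a difference in proportions but names only logistic regression, whose odds ratio and Wald interval fail against a group with no responders; a risk difference with a score-type interval fits better

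*Combined protocol and SAP*

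**What the plan says.** Section 9.3.4 of the protocol first describes the case in which everyone completes dosing. The estimand is then the mean difference in change to Day 57. It continues: "If however, intercurrent events are observed, three different strategies will be employed to handle early treatment discontinuation".

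- **Composite strategy (ITT).** It is used for endoscopy and overall disease activity, "to estimate the difference in the proportion of responders between dose groups". Response requires a set improvement without early discontinuation, and "Treatment failure is defined as non-response or early treatment discontinuation". With nothing missing, "this can be analyzed using logistic regression with dose group as a factor"; otherwise an unspecified imputation method applies. The section does not say how the logistic fit becomes a difference in proportions.
- **Treatment-policy strategy (ITT).** For change scores, "this can be achieved using Analysis of Covariance (ANCOVA) with dose group as a factor".
- **On-treatment strategy (per-protocol).** "In the absence of missing data this can be achieved using ANCOVA with dose group as a factor".

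The same section says "Change from baseline to Day 57 will be analyzed and reported descriptively". Section 9.1 marks hypotheses as not applicable, and Section 9.2 says the sample size was not based on power. Allocation is 4:1, with up to 65 participants in cohorts of about 8 active and 2 placebo (Sections 4.1 and 9.2). I found no statement on whether placebo participants form one group across dose levels in the efficacy comparisons.

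**The concern.** The composite estimand is on one scale and the named model is on another. Logistic regression reports odds ratios by default. If a group has no responders, the maximum-likelihood log odds for that group runs to minus infinity, so the odds ratio against it and its Wald interval cannot be interpreted. The groups are small, the placebo group is the smallest, and early discontinuation counts as failure, so an empty group is a realistic outcome.

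At stake is how a preliminary efficacy result would be reported. If placebo were empty, every dose-versus-placebo odds ratio would fail together, and a substitute method would be chosen after the data had been seen.

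A smaller point concerns the two change-score models. They are called analysis of covariance but name only the factor, so the covariate has to be guessed.

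**Working it through.** **Inputs from the protocol.** Up to 65 participants at 4:1 gives 65 × 0.2 = 13 placebo and 65 × 0.8 = 52 active. I take the active participants as 17, 17 and 18 over three dose levels. That split is an assumption, as are all responder and discontinuation rates below, because the documents give none.

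**The plan's own figure.** Section 9.2 gives the chance of seeing at least one event with a true rate of 20%. 1 − 0.8^8 = 0.832 and 1 − 0.8^4 = 0.590 match the stated 83% and 59%. No such figure is given for efficacy.

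**Step 1: is the composite analysis likely to be used?** The chance of at least one early discontinuation among 65 is 1 − (1 − r)^65. For r = 1%, 2%, 5% and 10% this is 0.480, 0.731, 0.964 and 0.999.

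**Step 2: chance of no responders, (1 − p)^n.**

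| Group | p = 10% | p = 20% | p = 30% |
|---|---|---|---|
| Placebo pooled, n = 13 | 0.254 | 0.055 | 0.010 |
| Active, one cohort, n = 8 | 0.430 | 0.168 | 0.058 |
| Placebo, one cohort, n = 2 | 0.810 | 0.640 | 0.490 |

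If 20% discontinue independently of response and count as failures, p falls to 8%, 16% and 24%, and the pooled-placebo figures become 0.338, 0.104 and 0.028. If those who stop would not have responded anyway, the figures stay as in the table.

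With placebo at 10% and each dose at 20%, the chance that at least one of the four groups is empty is 1 − (1 − 0.9^13)(1 − 0.8^17)²(1 − 0.8^18) = 0.30.

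**Step 3: what the two methods give, illustrative 4/17 active versus 0/13 placebo.**

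- Logistic regression: log odds ratio 21.4, SE 13,367, p = 0.999 at default stopping. The estimate is an artefact of when the iterations stop: it is 10.4, 25.4 and 35.7 at limits of 10, 25 and 50 iterations. The fitted proportions remain 0.235 and essentially 0, so the point difference survives.
- Newcombe: the Wilson limits are 0.0956 to 0.4726 for 4/17 and 0 to 0.2281 for 0/13. The difference is d = 4/17 − 0 = 0.235.
  - Lower limit: 0.2353 − √[(0.2353 − 0.0956)² + 0.2281²] = 0.2353 − 0.2675 = −0.03.
  - Upper limit: 0.2353 + (0.4726 − 0.2353) = 0.47.
- Miettinen-Nurminen: −0.02 to 0.48.

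At 0/17 versus 0/13 Newcombe still gives −0.23 to 0.18. Its exact coverage for 17 versus 13 was 0.950 to 0.986 over five assumed pairs of rates (active/placebo 0.1/0.1, 0.2/0.1, 0.3/0.1, 0.4/0.2, 0.5/0.3).

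**Step 4: does pooling matter?** For one cohort, take 2/8 versus 0/2. The Wilson limits are 0.0715 to 0.5907 and 0 to 0.6576, so Newcombe runs from 0.25 − √(0.1785² + 0.6576²) = −0.43 to 0.59. That is finite but uninformative.

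**Step 5: the baseline covariate.** The variance with a baseline term, relative to the unadjusted change score, is (1 − ρ²)/(1 + k² − 2ρk), where k is baseline SD over follow-up SD. At ρ = 0.5 it is 0.75, 0.92 and 1.00 for k = 1, 0.75 and 0.5. MCS-ES must be 2 or 3 at entry (Section 5.1), so its baseline SD is at most 0.5. If follow-up spread evenly over 0 to 3 (SD 1.118), k would be at most 0.447 and the ratio 0.75/0.753, or about 0.996: almost no gain.

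**The case against.** The strongest reply is that nothing essential is lost. With dose group as the only factor, the logistic model is saturated and its fitted proportions are the observed ones, so the stated estimand always has a point estimate. Section 9.3.4 promises no interval, test or p-value, the wording is permissive, and the analysis is descriptive. Reporting observed proportions and their differences would already comply. At response rates of 20% to 30% an empty pooled placebo group is also unlikely (5% to 1%). All of this stands, and it limits the weight of the point. It does not remove the mismatch: the only model named does not report the stated quantity, and it breaks down in a situation that these group sizes make possible.

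A reader might go further and infer that an empty group leaves no usable contrast at all. The documents do not support that: the raw difference remains, as do contrasts among groups with responders.

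A reader might also infer that the two ANCOVAs are really one-way ANOVAs on change, and so the wrong model. The protocol lists ANCOVA and ANOVA as separate abbreviations and, in Section 9.3.3, writes one-way analysis of variance where it means that. The natural reading is that the covariate was intended but left unnamed.

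Finally, comparing each dose only with placebo would be too narrow a remedy, because the target is the difference between dose groups. The fix covers that.

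**Conclusion.** The point holds as a mismatch of scale with a foreseeable failure. If early discontinuation occurs and a group has no responders, the log odds ratio and Wald interval against that group are not finite, and no method with an interval for the difference in proportions is named. For a pooled placebo group of about 13, the chance is 25%, 5% and 1% at response rates of 10%, 20% and 30%. These rest on assumed rates, full enrolment of 65, exact 4:1 allocation and pooling. A smaller study or unpooled placebo makes an empty group more likely.

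The ANCOVA wording is missing detail only. Efficacy here is a preliminary secondary objective without hypotheses, and no primary safety conclusion, dose decision or sample size is affected. This is a minor, inexpensive improvement.

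**What to change.** In Section 9.3.4:

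1. Replace the logistic model with the difference in responder proportions, for each dose versus placebo and between doses where they are compared. Give each a Newcombe or Miettinen-Nurminen 95% interval, reported descriptively.
2. State whether placebo is pooled across dose levels. With about 2 placebo participants per cohort, no interval method will be informative.
3. As a clarification, name the baseline value of the same score as the covariate in both ANCOVAs.

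The cost is wording. Baseline scores are already collected and the interval methods are standard. The covariate uses one degree of freedom: with 65 participants in four groups, the residual falls from 65 − 4 = 61 to 60. Its gain in precision may be near zero for MCS-ES.
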